- e. Justification for inclusion of a placebo or non-treatment group.

We have included a placebo control condition to assist with interpretation of the study results. Since this study will not be removing access to a known treatment, we believe that inclusion of the placebo condition poses low risk to participants.

- f. Definition of treatment failure or participant removal criteria.

Participants will be removed from the study if they remove their consent to participate, become pregnant, refuse to adhere to the study session schedule, or if it becomes clear that their continued participation could put them at increased risk (e.g., develop another chronic pain condition that requires treatment, onset of a medical/psychiatric disorder). These decisions will be made in conjunction with the study medical team.

- g. Description of what happens to participants receiving therapy when study ends or if a participant's participation in the study ends prematurely.

Because we will only be delivering study medications for assessment during visits and will not ask participants to stop taking their routine medications, there will be no need to taper the use of study medications or continue to monitor drug effects once participants are released.

5. Inclusion/Exclusion Criteria

Inclusion Criteria: 1) Age 45 or older, 2) meet the American College of Rheumatology criteria for knee OA, 3) report an average pain level of $\geq 3/10$, 4) not have taken any opioid medications for the past 30 days, 5) provide a urine sample that tests negative for illicit drugs and pregnancy, 6) be medically eligible to take study medications, 7) patients taking NSAIDs or acetaminophen must be on a stable dose for 30 days, 8) be fluent in English, and 9) willing to comply with the study protocol. We will enroll $\geq 50\%$ women because there is substantial evidence that men/women differ with regard to pain perception, endogenous cannabinoid receptor density, and response to opioids and will use sex as a covariate in analyses.

Exclusion Criteria: Individuals who 1) have cognitive impairment preventing completion of study assessment procedures, 2) meet current DSM-5 criteria for alcohol/substance use disorder, 3) meet criteria for lifetime history of opioid use disorder, 4) have taken stimulants, benzodiazepines, TCA, venlafaxine or duloxetine in the past seven days, 5) have a history of clinically significant cardiac arrhythmias or vasospastic disease, or an abnormal and clinically-significant ECG, 6) have history/current evidence of significant medical/ psychiatric illness that elevates risk for experiencing an adverse event (including current suicidal ideation), 7) have a known allergy to the study medications, or 8) are pregnant or breastfeeding. Additional exclusion criteria due to their effects on pain responses include 10) current peripheral neuropathy, 11) presence of Raynaud's phenomenon, 12) active vasculitis or severe peripheral vascular disease, 13) current infection, 14) confirmed diagnosis of periodic limb movement disorder or restless legs syndrome, 15) systemic inflammatory or autoimmune disorders such as rheumatoid arthritis, lupus, etc., 16) seizure disorder, or 17) have a chronic pain condition that produces pain greater than their KOA.

6. Drugs/ Substances/ Devices

- The rationale for choosing the drug and dose or for choosing the device to be used.

We have strategically selected hydromorphone and dronabinol for this study, both drugs will be encapsulated by the BPRU pharmacy to ensure double-blind administration, and placebo will consist of lactose or another benign weight-matched filler. See Table 1 above for drug dosing details.

i. *Hydromorphone (Dilaudid)* is a potent mu-opioid agonist that we have extensive experience administering in controlled laboratory settings. Hydromorphone is not subject to differences in CYP metabolic enzymes so will not require us to screen out individuals with recent exposure to CYP inhibitors/inducers, or to analyze/ statistically control for CYP metabolic profiles. The two (2 and 4 mg) oral doses of hydromorphone are commercially-available and regularly used for analgesia, which increases the clinical relevance of these results. We expect both doses of hydromorphone to exert a moderate analgesic effect on pain, which is an important feature because too strong a dose could overwhelm the cannabinoid effect and prevent us from effectively evaluating the study aims. Including both a low and moderate dose will provide an elegant assessment of whether a cannabinoid will produce an additive, synergistic, or no effect on the analgesic profile of hydromorphone.

ii. *Dronabinol (Marinol)* has been strategically chosen for this study because it is a widely-used, commercially-available Schedule II cannabinoid medication that is currently indicated for nausea and vomiting, and anorexia in AIDS patients, **but which could be prescribed off-label for the adjunctive treatment of clinical pain.** Dronabinol is a synthetic delta-9-tetrahydrocannabinol (THC) product (the primary psychoactive compound in cannabis sativa (marijuana)), and thus has generality with other THC compounds (such as smoked or edible marijuana products). When administered orally (as proposed here),

dronabinol reaches peak concentrations in 2-4 hours and is 90-95% absorbed but, due to extensive first-pass metabolism, is only 10-20% bioavailable. It is excreted in fecal (35-50%) and renal (10-15%) waste. The elimination half-life is biphasic, with an initial half-life of 4 hours and a terminal half-life of 25-36 hours, and an active metabolite (11-hydroxy-delta-9-THC) is produced. There is no current evidence that dronabinol is differentially affected by P450 status. Dronabinol is sold commercially in 2.5mg, 5mg, and 10mg dose ranges. **We have chosen to administer a 0 mg (placebo) and 10mg dose of dronabinol in this study**, which is within the range currently prescribed for chemotherapy-induced nausea and vomiting and AIDS-related anorexia, and therefore will have direct clinical applicability. Dronabinol will be purchased as a capsule and will be over-encapsulated by our research pharmacy to ensure double-blind administration procedures. Placebo doses will consist of lactose or another benign weight-matched filler.

Pharmacokinetic (pK) Analyses: Blood samples, drawn on a subset of participants, will enable direct comparison of serum drug levels with outcomes for the study aims (e.g., analgesia and physical functioning, subjective and observer- rated effects, abuse liability measures, and cognitive performance). We have chosen to sample pK at numerous timepoints to examine whether the duration of effects changes as a function of drug administration and determine whether behavioral changes following hydromorphone/dronabinol co-administration result from pharmacological enhancement or whether co-administration modifies the metabolic profile of either drug in such a way that it changes their duration of action. pK analysis is considered critical for this initial stage of evaluating drug-drug interactions¹³⁵ and will directly inform decisions regarding specific opioid/cannabinoid dose combinations that may be most appropriate to advance into clinical trials for the treatment of pain.

- b. Justification and safety information if FDA approved drugs will be administered for non-FDA approved indications or if doses or routes of administration or participant populations are changed.

Hydromorphone: Hydromorphone hydrochloride is a pure mu opioid agonist that can be administered in oral, rectal, intramuscular (IM) or intravenous (IV) formulations for the indication of acute and/or chronic pain. We have chosen to administer hydromorphone because we have extensive experience administering hydromorphone in all formulations^{96; 109-117}, and know that it will produce reliable and consistent results that will aid interpretation of outcomes. Hydromorphone was also selected as the exemplar opioid for this study because it is not subject to differences in CYP metabolic enzymes and therefore will not require us to screen out individuals with recent exposure to CYP inhibiting or inducing medications, or to analyze and statistically control for CYP metabolic profiles in individual subjects. There is also no apparent effect of gender on the pharmacokinetics of hydromorphone. We have selected a low and mid-level dose because they are within the range of doses approved by the FDA. They are also sensitive to the QST tests we have proposed, and we therefore believe both will provide an ideal opportunity to evaluate whether the curve of hydromorphone is shifted as a function of dronabinol administration.

Dronabinol: Dronabinol is a schedule II drug that is being administered at 10 mg, which is consistent with the range approved by the FDA for therapeutic use in patients with chemotherapy-induced nausea and vomiting, and loss of appetite in patients with advanced HIV (AIDS). Dronabinol is also used off label for the treatment of Gilles de la Tourett's syndrome, general loss of appetite (related to cancer), spasticity from Multiple Sclerosis, treatment refractory and postoperative nausea and vomiting, and treatment refractory pruritus. When administered orally (as proposed here), dronabinol reaches peak concentrations in 2-4 hours and is 10-20% bioavailable. It is subject to extensive first-pass metabolism and is excreted in fecal (35-50%) and renal (10-15%) waste, with an elimination half-life of 19-36 hours.

We have selected oral dronabinol because it is FDA approved for pain conditions and more likely than nabilone to be prescribed in practice due to cost. We believe this approach will yield data that can be instantly utilized by pain treatment specialists, which increases the generalizability of our study approach.

c. Justification and safety information if non-FDA approved drugs without an IND will be administered.

N/A

7. Study Statistics

a. Primary outcome variable:

Aim 1: Evaluate the magnitude and duration of cannabinoid/opioid combination to reduce clinical pain (Hyp1) and central sensitization (Hyp2). Hyp1 (pain VAS) and Hyp 2 (CS) will be analyzed using repeated 2-factor (Drug x Time) models that examine linear and quadratic effects as well as duration and magnitude, and direct and interaction effects. If large variation exists across subjects at baseline, then raw data will be transformed to change-from-baseline and analyzed in drug condition by time models. A secondary outcome will be peak change from baseline, analyzed as a function of Drug (1-factor model).

- Aim 2: Evaluate the degree to which physical functioning is altered by the cannabinoid/opioid combination.** Hyp3 will be assessed using the TUG and 6MWT. Time to complete the TUG task will be the primary outcome and will be evaluated using 2-factor (Drug x Time: Pre to Peak) models.
- Aim 3: Conduct a direct comparison of the subjective, physiological, abuse liability, and cognitive effects of the cannabinoid, opioid, and combination.** Hyp4 (adverse events) will be assessed by summing the mean number of related mild, moderate, and severe adverse events (separately) and using 1 factor models to assess a main effect of Drug. Hyp5 (abuse liability) will be assessed using the Drug vs. Money questionnaire and changes in VAS ratings using 2-factor models (Drug x Time). Hyp6 will evaluate changes in neurocognitive performance, including study session number as a covariate to control for practice effects, using 2-factor (Drug x Time) analyses. Secondary outcomes for this hypothesis will be analysis of peak change from baseline for the cognitive outcomes, analyzed using 1-factor (Drug) ANOVAs to evaluate a main effect of drug.
- Aim 4: Evaluate the pharmacokinetic (pK) and pharmacodynamic (pD) profile of the cannabinoid, opioid, and the combination in OA patients.** Hyp 7 (pK) will be assessed by evaluating Cmax (maximum concentration) and Tmax (time to maximum concentration) as a function of Drug condition using 1-factor models. We will also examine linear and quadratic effects to evaluate the time course of concentration. Linear and quadratic effects will be modeled for Hyp8 (pD) and analyzed by evaluating VAS and physiological ratings, transformed to change from baseline, evaluating area under the curve and peak change from baseline to identify main effects of the Drug condition. We will then conduct multivariate regression analyses to evaluate the degree to which the Cmax and Tmax correlate with pharmacodynamic outcomes, including abuse liability ratings, VAS ratings of drug effects, and cognitive testing outcomes.

Statistical analyses will be conducted separately by Phase and use multilevel analyses with an autoregressive (AR1) or compound symmetry (CS) covariance structures (as appropriate for the data set) using SAS PROC MIXED¹³⁷. Interpretation of drug condition main effects and interactions will rely on Tukey post-hoc tests. Statistical significance will be set at $p < 0.05$.

Expected Outcomes: We expect that dronabinol will enhance hydromorphone-induced analgesia to both clinical and laboratory-evoked pain. Our comprehensive battery of rigorous, testing procedures provides an opportunity to test effects on multiple mechanisms of experimentally-induced pain. We also expect improvement in physical functioning under combined dosing, and that the addition of the cannabinoid will not significantly increase the overall abuse liability or adverse event profile. We do suspect the cannabinoid may have cognitive effects (though the degree to which this may happen is not clear).

b. Secondary outcome variables.

Demographic and drug use characteristics that are hypothesized a priori to be associated with outcomes (e.g., Body Mass Index) will be compared across sex groups and significant differences will be included as covariates in the subsequent analyses. All analyses will be repeated and sex (male/female) will be added as a factor to the analyses.

c. Statistical plan including sample size justification and interim data analysis.

This will be the first study to examine interactions between cannabinoids and opioids on clinical and laboratory-evoked measures of pain in a population who has chronic pain and central sensitization. The study uses a within-subject, placebo-controlled design and no data exist upon which to generate a power analysis. We have selected two primary outcomes for the measurement of analgesia: measures of conditioned pain modulation and time to hand withdraw latency in a cold presser test.

[name], a biostatistician with extensive experience analyzing within-subject laboratory tests of drug effects, conducted a revised power calculation based on new literature that employs methods similar to those of this study (Cooper et al., 2018). Sample size estimates were premised with a power of 0.8, alpha =0.05 and calculated effect sizes (Cohen, 1988). These analyses suggests a sample size ranging from 10-15 individuals would be sufficient to detect large effect sizes. Because one of our aims focuses on a sex-comparison, we originally planned to double our enrollment. Thus, our sample of 64 completers (32/sex) will yield sufficient power to evaluate direct effects of study condition on CPM and cold presser in both Phases, even at small effect size levels, and will also be sufficient to identify between-session differences on pK results¹⁴⁰.

d. Early stopping rules.

The safety of participants is the highest priority. The largest potential risk of this study is cardiovascular in nature. This notion is based upon the results of a published study that reported an increase in heart rate and blood pressure among patients exposed to the cannabinoid dronabinol who were also undergoing opioid withdrawal (of which increased heart rate and blood pressure is a known symptom). This group differs from our target population in many ways, however out of an abundance of caution in these early studies, we will use this experience to inform our safety criteria. We will monitor vital signs at all study data collection time points and will follow procedures that we have developed and successfully used in previous studies that administered drugs (e.g., cocaine) with known cardiovascular risks. Specifically, if a participant's parameters reach these thresholds, then a study physician, who will always be available via telephone, will be contacted and consulted to determine the appropriate course of action.

- Systolic blood pressure: $\geq 180\text{mm Hg}$

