
2. Objectives (include all primary and secondary objectives)

Aim 1: Evaluate the magnitude and duration of cannabinoid/opioid combination to reduce clinical pain and central sensitization. We hypothesize the cannabinoid/opioid combination will increase the

magnitude and duration of analgesia in clinical pain report (Hyp1) and QST-derived central sensitization (Hyp2), relative to each drug administered alone and relative to placebo.

Aim 2: Evaluate the degree to which physical functioning is altered by the cannabinoid/opioid combination. We hypothesize that the drug combination will improve physical function (Hyp3) relative to the drugs administered alone and placebo.

Aim 3: Compare the subjective, physiological, abuse liability, and cognitive effects of the cannabinoid, opioid, and combination. We hypothesize that cannabinoids will not increase adverse events (Hyp4), or abuse liability (Hyp5: ratings of positive drug effects) relative to opioids alone and that the cannabinoid (alone and in combination with opioids) will reduce neurocognitive performance (Hyp6), relative to the opioid alone and placebo.

Aim 4: Evaluate the pharmacokinetic and pharmacodynamic profile of the cannabinoid, opioid, and the combination in OA patients. We hypothesize that the combined dose will result in an altered pharmacokinetic (Hyp7) /pharmacodynamics profile (Hyp8) compared to either drug alone.

3. Background (briefly describe pre-clinical and clinical data, current experience with procedures, drug or device, and any other relevant information to justify the research)

This laboratory study is the first step in addressing an important and timely public health problem: Can cannabinoids enhance the analgesic efficacy of an opioid and ultimately reduce opioid dosing in people with chronic pain?

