Study Design Overview: We propose to study the separate and combined effects of the FDA-approved cannabinoid dronabinol (Marinol) and the prototypical opioid hydromorphone (Dilaudid). Following telephone and screening to establish study eligibility, a cohort of **n=100** adults with knee osteoarthritis (KOA) will complete four different within-subject experimental sessions. Participants will complete one of two Phases, receiving either a 4mg or 2mg dose of hydromorphone. Randomization will be split equally across the two Phases. During each session, participants will complete baseline QST, questionnaires, and a neurocognitive battery. Oral hydromorphone will be administered in the first session. Subsequent sessions will consist of 1 of 3 conditions, and session order will be randomized and counter-balanced. Conditions will be 1) placebo; 2) oral dronabinol (10mg); and 3) combined hydromorphone and dronabinol (10mg). Measures will be repeated throughout the session to fully characterize the drug effects. Participants and staff will be kept blinded to the study medications under investigation, and participants will be informed in the consent form they may receive a combination of FDA-approved stimulants, benzodiazepines, opioids, cannabinoids, over-the-counter medications or placebo, though the participants will not actually be receiving stimulants, benzodiazepines, or over-the-counter drugs. All participants will be provided with transportation to and from the experimental sessions. Primary outcomes are measures of clinical pain, central sensitization, physical function and drug effects/adverse events. A subset of participants will undergo blood draws for pharmacokinetic (pK) profile. This will be voluntary and should aid recruitment as those that do not want an IV will still be allowed to participate in the study. We will aim to recruit 30 participants that volunteer to undergo IV/blood drawing procedures in order to characterize pK.

Phase 1: The initial Phase of this project will include hydromorphone at a dose of 4mg.

Phase 2: The second Phase of this project will include hydromorphone at a dose of 2mg in order to evaluate drug effects at a reduced opioid dose.

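### Hyp4 and Hyp5 assert no increase relative to the opioid alone, but the plan has only difference tests, which can refute that claim but cannot support it

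*Combined protocol and SAP*

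**What the plan says.** Section 2, Aim 3 sets out the two hypotheses: "We hypothesize that cannabinoids will not increase adverse events (Hyp4), or abuse liability (Hyp5: ratings of positive drug effects) relative to opioids alone".

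Section 7.a, Aim 3 gives the analyses. For Hyp4 it takes related mild, moderate and "severe adverse events (separately) and using 1 factor models to assess a main effect of Drug". Hyp5 "will be assessed using the Drug vs. Money questionnaire and changes in VAS ratings using 2-factor models (Drug x Time").

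The closing paragraph of the same section adds two general rules: "Statistical analyses will be conducted separately by Phase and use multilevel analyses", and "Interpretation of drug condition main effects and interactions will rely on Tukey post-hoc tests". Significance is p<0.05, with sidedness not stated. Under Expected Outcomes the investigators anticipate that "the addition of the cannabinoid will not significantly increase the overall abuse liability or adverse event profile".

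No section gives a non-inferiority or equivalence margin, a confidence-interval rule or a power statement for adverse events or abuse liability. The sample-size text in section 7.c concerns conditioned pain modulation, the cold pressor test and pharmacokinetics.

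On the reference condition, section 4.a says: "Oral hydromorphone will be administered in the first session".

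**The concern.** Most of the hypotheses predict a change, which a difference test can support. Hyp4 and Hyp5 predict the absence of an increase. For these, a non-significant Tukey comparison is what one would see if there were no increase, and also what one would often see if there were a modest increase and too few participants to detect it. The planned analysis does not separate the two cases.

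The Abstract says the findings will be critical to judging the efficacy and safety of the combination before it moves to clinical trials. If a non-significant result were carried forward as reassurance, a small or moderate rise in adverse events or drug liking could go with it.

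**Working it through.** **Inputs from the documents.** Four within-subject conditions; Tukey at 0.05; analysis by Phase; 100 enrolled and split equally between Phases (section 4.a); 64 completers (section 7.c). The number per Phase is therefore 32 if the 64 are split, 50 if all 100 complete, or 64 if that figure is meant per Phase.

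**Assumptions.** The documents give no effect size, SD or event rate for these outcomes. Effects below are in SDs of the within-person difference (d), for one paired contrast under compound symmetry, one of the two covariance structures the plan allows. Tests are two-sided.

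**1. The plan's own figure.** Section 7.c says 10-15 people suffice for large effects at power 0.8 and alpha 0.05. A paired t-test needs 15 at d=0.8, 12 at d=0.9 and 10 at d=1.0, so the figure reproduces if large means about 0.8 to 1.0. It does not cover small or moderate rises, or these outcomes.

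**2. How often Tukey misses a real rise.** The critical value is c = q(0.95; 4, df)/√2 with df = 3(n-1). The miss probability is P(T ≤ c), where T is noncentral t with noncentrality d√n.

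| n per Phase | df | c | d=0.3: d√n, miss | d=0.5: d√n, miss |
|---|---|---|---|---|
| 32 | 93 | 2.616 | 1.70, 81% | 2.83, 41% |
| 50 | 147 | 2.599 | 2.12, 68% | 3.54, 18% |
| 64 | 189 | 2.592 | 2.40, 57% | 4.00, 8% |

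At d=0.8 and n=32 the miss rate is 3%, so large rises in rated outcomes would rarely be overlooked.

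**3. What a non-significant result leaves open.** The half-width of an unadjusted 95% interval is t(0.975, n-1)/√n: 2.040/√32 = 0.36, 2.010/√50 = 0.28 and 1.998/√64 = 0.25 SD.

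**4. Adverse events.** Suppose 3 of 32 participants have one event each on the combination and nobody has one in any other condition.
- Planned Gaussian model: difference 3/32 = 0.094; residual mean square 2.039/93 = 0.0219; standard error √(2 × 0.0219/32) = 0.0370; t = 2.53, below 2.616; Tukey p=0.061.
- Paired score interval: the limits are the values Δ at which (b - c - nΔ)/√{n[2q + Δ(1-Δ)]} = ±1.96, with b=3, c=0, n=32 and q the constrained estimate of the probability of an event on hydromorphone only. This gives -2 to +24 percentage points.

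The result is non-significant and yet compatible with a rise affecting nearly a quarter of participants.

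**5. What a margin would demand.** With no true difference, the chance that the upper 95% limit falls below a margin m is P(T > t(0.975, n-1)), with noncentrality m√n and df n-1. For margins of 0.3 and 0.5 SD this is 38% and 78% at n=32, and 55% and 93% at n=50. About 90 per Phase are needed for 80% at 0.3 SD. If two independent outcomes must both pass at n=32, the figures are 0.376² = 14% and 0.782² = 61%; positive correlation would raise them.

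**The case against.** The strongest reply is that no misuse is planned. Aim 3 sets out to compare, the hypotheses are directional expectations, and the phrase about no significant increase sits under Expected Outcomes, not in a decision rule. This is a first-step laboratory study, and no section makes Hyp4 or Hyp5 a gate for advancing the combination. That stands. A reader might infer that the investigators intend p>0.05 as proof of no increase, but the documents do not say so. What remains is that the hypotheses are worded as claims the analysis cannot support, and the only success wording refers to significance.

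It is also fair that every effect above is assumed, that a single contrast simplifies the repeated ratings in Hyp5, and that the event example uses one event per participant where the plan counts events.

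A reader might further infer that the fixed session order tilts the comparison towards reassurance. Hydromorphone alone always comes first, section 8.b allows participants with untoward effects to be excluded after it, and session number is named as a covariate only for Hyp6 ("including study session number as a covariate to control for practice effects"). But the documents give no direction for an order effect, exclusion is an option and not a rule, and no completers-only analysis is specified. This is a limitation to state, not a demonstrated bias.

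**Conclusion.** The mismatch is real and should be corrected. As written, the analysis can refute Hyp4 and Hyp5 but cannot support them. Under the assumptions shown, a 0.3 SD rise would be non-significant in 57% to 81% of trials and a 0.5 SD rise in 8% to 41%, depending on how many complete each Phase. The mismatch itself does not depend on these figures; only its size does.

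A reader might infer that a paired score interval would also be the more sensitive tool for adverse events. That does not follow. Simulating 10% background against 20% on the combination at n=32, the unadjusted score interval misses the rise 82% of the time against 90% for the Tukey test, but the gap comes from the missing adjustment. At equal adjustment the score method misses more: 82% against 76% unadjusted, and 95% against 90% at the Tukey level. The case for it is that Gaussian p-values are unreliable with sparse counts.

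**What to change.** In sections 2 and 7.a:

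- Restate Hyp4 and Hyp5 as estimation, and say that p>0.05 will not be read as no increase.
- Report combination minus hydromorphone with a 95% confidence interval for each outcome and Phase. Add dronabinol minus hydromorphone if Aim 3 is meant to include the cannabinoid alone.
- For adverse events, by severity, add the paired difference in the proportion of participants with an event, with an interval suited to sparse paired data such as a score interval. Say that it is not adjusted for multiplicity.
- Allow a claim of no increase only if the investigators fix and justify a margin before unblinding, state which outcomes must meet it, and the upper limit falls below it. Otherwise report the result as inconclusive.
- State as a limitation that hydromorphone alone is always session 1 and that participants may be excluded after it. Neither an interval nor a margin removes this.

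The cost is wording and reporting, with no extra data or participants. The price is a weaker claim, or one that is harder to support: even with no true difference, a 0.3 SD margin would be met for a single outcome only 38% of the time at 32 per Phase, and less often if several outcomes must all meet it.

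### The cohort of 100 and the 64 completers are never reconciled, and power is claimed at 64 although each Phase, analysed alone, would have about 32 or 50 completers

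*Combined protocol and SAP*

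**What the plan says.** Section 4a (Study Design Overview) describes the sample as 100 "adults with knee osteoarthritis (KOA) will complete four different within-subject experimental sessions". It then divides that sample: "Participants will complete one of two Phases, receiving either a 4mg or 2mg dose of hydromorphone", and "Randomization will be split equally across the two Phases".

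Section 7c (sample size justification) uses another number: "Thus, our sample of 64 completers (32/sex) will yield sufficient power to evaluate direct effects of study condition". That sentence goes on to claim adequacy for conditioned pain modulation and the cold pressor in both Phases, down to small effects. The stated premises are: "Sample size estimates were premised with a power of 0.8, alpha =0.05 and calculated effect sizes". The same section says that 10 to 15 people suffice for large effects and that enrolment was to be doubled because of the sex comparison. It gives no numeric effect size, standard deviation, within-person correlation or dropout rate.

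The analysis text at the end of section 7a says: "Statistical analyses will be conducted separately by Phase".

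**The concern.** Two sample sizes stand in the current text with nothing joining them. If 100 is the number enrolled, the plan carries an unstated loss of more than a third. If 100 is the number completing, the power statement uses the wrong figure.

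The more consequential point is the unit of analysis. The Phases are separate groups of people and each is analysed alone, so no by-Phase drug comparison can use 64 people under a cohort of 100 split equally. The power statement nevertheless quotes 64 and claims adequacy in both Phases. A reader would take the precision of each Phase to be better than it is, and might read a null result in one Phase as evidence against a small effect that the Phase was unlikely to detect.

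**Working it through.** **Inputs from the document.** Cohort 100 (section 4a); completers 64, 32 per sex (7c); one Phase per person and an equal split (4a); analysis by Phase (7a); power 0.80 and alpha 0.05 (7c).

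**Assumptions, because the plan is silent.** Two-sided testing; a simple paired contrast between two drug conditions; differences d in units of the SD of the within-person difference, with 0.2 for small and 0.8 to 1.0 for large.

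**1. The plan's own base figure.** Paired t-test power comes from the noncentral t distribution with n − 1 degrees of freedom and noncentrality d√n. For 80% power, d = 0.8 needs n = 15 and d = 1.0 needs n = 10. The stated 10 to 15 for large effects is therefore reproduced under these assumptions.

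**2. From the base figure to 64.** Doubling gives 2 × 10 = 20 to 2 × 15 = 30. Doubling within each of two Phases gives 40 to 60. Neither gives 64. Sixteen per sex per Phase would (16 × 2 × 2 = 64), but the plan does not state this. No derivation of 100 is given.

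**3. From 100 to 64.** Implied loss is 1 − 64/100 = 36%. For comparison, 64 completers at 20% loss would need 64/0.80 = 80 enrolled, and at 30% loss 64/0.70 = 91.4, so 92.

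**4. Completers per Phase.**
- All 100 complete: 100/2 = 50.
- 64 is the total and losses are equal: 64/2 = 32.
- 64 is meant per Phase: 2 × 64 = 128 completers, more than the cohort of 100, so this reading is excluded.

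**5. Power at each number** (two-sided paired t, alpha 0.05):

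| n | Detectable d at 80% power | Power at d = 0.2 | Power at d = 0.5 | Power at d = 0.8 |
|---|---|---|---|---|
| 32 | 0.51 | 20% | 78% | 99% |
| 50 | 0.40 | 28% | 93% | >99% |
| 64 | 0.36 | 35% | 98% | >99% |

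At d = 0.2 the noncentrality is 0.2 × √32 = 1.13 at n = 32 and 0.2 × √50 = 1.41 at n = 50. Eighty per cent power at d = 0.2 would need 199 people in a Phase.

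**6. A more favourable test.** For an overall F test across the four conditions at f = 0.1, with noncentrality n × 4 × f²/(1 − ρ), power depends on the within-person correlation ρ:

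| n | ρ = 0.5 | ρ = 0.7 | ρ = 0.8 | ρ = 0.9 |
|---|---|---|---|---|
| 32 | 23% | 37% | 53% | 85% |
| 50 | 35% | 55% | 75% | 97% |
| 64 | 44% | 68% | 86% | 99% |

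Of the correlations tried, only 0.9 takes a Phase of 32 or 50 past 80%. At 64 a correlation of 0.8 is already enough, so using 64 in place of the per-Phase number changes the answer. The plan states no correlation.

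**The case against.** The strongest reply is that the two numbers do not conflict. The protocol routinely says that participants will complete the procedures scheduled for them, as in the visit count in section 4b, and only section 7c uses the noun completers. A planned cohort of 100 with 64 expected to finish is a natural reading. Loss is also foreseen: medical eligibility is settled just before dosing at the first session (4a), people with untoward effects at that session can be excluded from further sessions (8b), and removal and withdrawal are covered (4f). This stands as far as it goes: the gap may be an unlabelled enrolment target. But the document never says so and never quantifies the loss, and this reading leads to 32 per Phase, the less favourable number.

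A second reply is that the equal split already fixes allocation. That is right: 50 per Phase follows from 100. What remains open is completers per Phase.

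A third is that the plan uses mixed Drug × Time models with Tukey comparisons, not a single paired t-test, and that for large effects 32 and 50 are both ample. Both points are fair. The paired figures are a benchmark under stated assumptions. The plan's claim, however, extends to small effects, and it gives no input that would show a mixed model closing that gap.

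A reader might go further and infer two rival recruitment targets, with enrolment free to stop at either, or testing at one number and again at the other with an inflated false-positive rate. The documents do not support this. They plan no efficacy look at either number; the one early data review described is a check for tachycardia after 5 participants (8b).

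**Conclusion.** The point holds as a labelling gap plus a power statement made at the wrong number. The document does not say whether 100 is enrolled or completed and states no loss. The number relevant to each analysis is 32 or 50 per Phase, not 64. On a two-sided paired contrast at alpha 0.05, that means a detectable difference of 0.51 or 0.40 SD, and 20% or 28% power at an assumed 0.2 SD. The claim of sufficient power at small effects in both Phases is therefore unsupported by a simple paired contrast on either reading; under an overall F test it would need a very high within-person correlation that the plan does not give.

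The figure of 32 assumes that 64 is the total and that losses are equal between Phases. The effect sizes are assumptions, because the plan gives none. Large effects are well covered at either number. By-Phase precision is bounded by these two cases, so it would be wrong to call it wholly undetermined.

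**What to change.** In sections 4a and 7c, use one number labelled as enrolled (or randomized) and one labelled as completed, the same in both places. State the assumed loss; if the intended pair is 100 and 64, that is 36%. Give completers per Phase.

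Replace the current sufficiency claim in 7c with power, or the difference detectable at 80% power, for the per-Phase completer number. State the effect size, sidedness, test and within-person correlation used. If the small-effect claim is to be kept, show the calculation that supports it at that number; otherwise withdraw it.

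The cost is protocol wording and a short recalculation. The stated power will probably look less favourable. No extra participants and no change of procedure are needed.
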